### **5.6 Participant Replacement Strategy**

In order to adequately evaluate the safety of the doses administered in this study, all participants enrolled must meet the criteria for evaluability for Cycle 1. Participants are considered nonevaluable and will be replaced if:

- They are allocated but not treated.
- They discontinue from the trial prior to completing all the safety evaluations for reasons other than treatment-related AEs.
- They receive less than 75% of the total selumetinib or MK-8353 study treatment in Cycle 1 and did not experience a DLT.

Participants who are not evaluable will be replaced unless accrual to the dose level has stopped. Nonevaluable participants will not be counted toward the total number of participants in the dose level for DLT evaluation.

If a participant experiences a DLT in Cycle 1, study intervention may be discontinued following discussion between the Sponsor and investigator. However, if the participant is deriving clinical benefit from the study intervention, the participant may be allowed to continue after discussion between the Sponsor and the investigator.

## 6 STUDY INTERVENTION

Study intervention is defined as any investigational intervention(s), marketed product(s), placebo, or medical device(s) intended to be administered to a study participant according to the study protocol.

Study interventions provided by the Sponsor will be packaged to support enrollment and replacement participants as required. When a replacement participant is required, the Sponsor or designee needs to be contacted prior to dosing the replacement supplies. Clinical supplies will be labeled with guidance to administer as directed.

## 6.1 Study Intervention(s) Administered

The study intervention(s) to be used in this study are outlined in [Table 4](#).

Table 4 Study Interventions

Arm Name	Arm Type	Intervention Name	Type	Dose Formulation	Unit Dose Strength(s)	Dosage Level(s)	Route of Administration	Regimen/ Treatment Period/ Vaccination Regimen	Use	IMP/ NIMP	Sourcing
MK-8353 + MK-5618	Experimental	MK-8353	Drug	Capsule	50 mg, 100 mg	50 mg, 100 mg, 150 mg, 200 mg, 250 mg	Oral	BID 4 days on and 3 days off	Experimental	IMP	Provided centrally by Sponsor
MK-8353 + MK-5618	Experimental	MK-5618 (Selumetinib)	Drug	Capsule	25 mg	25 mg, 50 mg, 75 mg, 100 mg, 125 mg	Oral	BID 4 days on and 3 days off	Experimental	IMP	Provided centrally by Sponsor

BID = Twice daily; IMP = Investigational Medicinal Products; NIMP = Non-investigational Medicinal Product

Alternate dose levels, drug administration frequency and dosing schedule (eg, BID vs. once daily [QD], on/off intermittent dosing schedule) may be explored.

All supplies indicated in [Table 4](#) will be provided per the "Sourcing" row depending upon local country operational requirements. Every attempt should be made to source these supplies from a single lot/batch number. The study site is responsible for recording the lot number, manufacturer, and expiry date for any locally purchased product per local guidelines unless otherwise instructed by the Sponsor.

Refer to Section 8.1.8 for details regarding administration of the study intervention.

## **6.2 Preparation/Handling/Storage/Accountability**

### **6.2.1 Dose Preparation**

There are no specific calculations or evaluations required to be performed in order to administer the proper dose to each participant. The rationale for selection of doses to be used in this study is provided in Section 4.3.

### **6.2.2 Handling, Storage, and Accountability**

The investigator or designee must confirm appropriate temperature conditions have been maintained during transit for all study intervention received, and any discrepancies are reported and resolved before use of the study intervention.

Only participants enrolled in the study may receive study intervention, and only authorized site staff may supply or administer study intervention. All study interventions must be stored in a secure, environmentally controlled, and monitored (manual or automated) area in accordance with the labeled storage conditions with access limited to the investigator and authorized site staff.

The investigator, institution, or the head of the medical institution (where applicable) is responsible for study intervention accountability, reconciliation, and record maintenance (ie, receipt, reconciliation, and final disposition records).

For all study sites, the local country Sponsor personnel or designee will provide appropriate documentation that must be completed for drug accountability and return, or local discard and destruction if appropriate. Where local discard and destruction is appropriate, the investigator is responsible for ensuring that a local discard/destruction procedure is documented.

The study site is responsible for recording the lot number, manufacturer, and expiry date for any locally purchased product (if applicable) as per local guidelines unless otherwise instructed by the Sponsor.

The investigator shall take responsibility for and shall take all steps to maintain appropriate records and ensure appropriate supply, storage, handling, distribution, and usage of study interventions in accordance with the protocol and any applicable laws and regulations.

## **6.3 Measures to Minimize Bias: Randomization and Blinding**

### **6.3.1 Intervention Assignment**

Treatment allocation will occur centrally using an interactive response system / integrated web response system (IRS/IWRS). Participants will first be assigned in a nonrandom fashion to the diagonal dose combination sequence. Once this sequence is closed and in case two additional off-diagonal dose combination sequences are initiated, participants will be allocated by alternate assignment to either off-diagonal sequence. In each sequence, a new dose combination will open for enrollment without delay once the 21-day DLT observation

period of the previous dose combination level is completed. Dose escalation decisions within each sequence will be made independently.

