## 6.6.2 Definition of Dose limiting Toxicity

All toxicities will be graded using NCI CTCAE v4.0 based on the investigator assessment.

The DLT window of observation will be during Cycle 1. The observation window can be modified to encompass Cycle 1 and 2 (and/or additional cycles).

The occurrence of any of the following toxicities during Cycle 1 will be considered a DLT, if assessed by the investigator to be possibly, probably, or definitely related to study treatment administration.

1. Grade 4 nonhematologic toxicity (not laboratory).
2. Grade 4 hematologic toxicity lasting  $\geq 7$  days, except thrombocytopenia:
  - Grade 4 thrombocytopenia of any duration
  - Grade 3 thrombocytopenia associated with clinically significant bleeding
3. Any nonhematologic AE  $\geq$  Grade 3 in severity should be considered a DLT, with the following exceptions: Grade 3 fatigue lasting  $\leq 3$  days; Grade 3 diarrhea, nausea, or vomiting without use of anti-emetics or anti-diarrheals per SOC lasting  $< 72$  hours; Grade 3 rash without use of corticosteroids or anti-inflammatory agents per SOC.
4. Any Grade 3 or Grade 4 non-hematologic laboratory value if:
  - Clinically significant medical intervention is required to treat the subject, or
  - The abnormality leads to hospitalization, or
  - The abnormality persists for  $\geq 72$  hours.
  - The abnormality is consistent with drug-induced liver injury and meeting the protocol Events of Clinical Interest criteria (see Section 8.4.7)

Exceptions: Clinically nonsignificant, treatable, or reversible laboratory abnormalities including liver function tests, uric acid, etc.

5. Febrile neutropenia Grade 3 or Grade 4:
  - Grade 3 is defined as absolute neutrophil count (ANC) <1000/mm^3 with a single temperature of >38.3 degrees C (101 degrees F) or a sustained temperature of ≥38 degrees C (100.4 degrees F) for more than 1 hour
  - Grade 4 is defined as ANC <1000/mm^3 with a single temperature of >38.3 degrees C (101 degrees F) or a sustained temperature of ≥38 degrees C (100.4 degrees F) for more than 1 hour, with life-threatening consequences and urgent intervention indicated.
6. An elevated AST or ALT laboratory value that is ≥3X the ULN and an elevated total bilirubin laboratory value that is ≥2X the ULN and, at the same time, an alkaline phosphate laboratory value that is <2X the ULN, as determined by the way of protocol-specified laboratory testing or unscheduled laboratory testing.

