7. Prolonged delay (>2 weeks) in initiating Cycle 2 due to treatment-related toxicity.
8. Any treatment-related toxicity that causes the participant to discontinue treatment during Cycle 1.
9. Missing >25% of MK-8353 and/or selumetinib doses as a result of drug-related AE(s) during the first cycle.
10. Grade 5 toxicity.
11. Cardiac disorders
  - Absolute decrease in LVEF >10% compared with baseline and the LVEF is below the institution's lower limit of normal
  - Left ventricular systolic dysfunction Grade ≥3
  - Other cardiac disorders Grade ≥3
12. Vascular disorders
  - Hypertension CTCAE Grade ≥3 requiring more than 1 drug or more intensive therapy
  - Grade 4 hypertension

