Grade 1-2	Maintain dose level of MK-8353 and selumetinib and increase frequency of ophthalmic monitoring to at least 14 days until stabilization or resolution.
Grade 3	Interrupt MK-8353 and selumetinib and refer participant to ophthalmologist within 1 week: If resolved to Grade $\leq 1$ in $\leq 21$ days, reduce 1 dose level of MK-8353 and selumetinib. If not resolved to Grade $\leq 1$ in $\leq 21$ days, permanently discontinue MK-8353 and selumetinib.
Grade 4	Permanently discontinue MK-8353 and selumetinib.

Liver-related Adverse Events	
Grade 1 AST or ALT (> ULN - 3 × ULN)	Maintain dose level of MK-8353 and selumetinib.
Grade 2 AST or ALT (>3 - 5.0 × ULN) or 3 × baseline value (if liver metastasis) AND blood bilirubin ≤2.0 × ULN	Interrupt dose of MK-8353 and selumetinib until resolved to Grade ≤1 (or Grade ≤2 in case of liver metastasis), then: 
 
• If resolved in ≤14 days, maintain dose level of MK-8353 and selumetinib.
 
• If resolved in >14 days, reduce dose level of MK-8353 and selumetinib.
 
 Recurrence: 
 
• Interrupt dosing of MK-8353 and selumetinib until resolved to Grade ≤1 (or Grade ≤2 in case of liver metastasis), then resume treatment at a reduced dose.
 

Grade 2 AST or ALT (> 3 - 5.0 × ULN) or 3 × baseline value (if liver metastasis) AND blood bilirubin > 2.0 × ULN	Interrupt dose of MK-8353 and selumetinib until resolved to Grade ≤1 (or Grade ≤2 in case of liver metastasis), then: 
 
• If resolved in ≤7 days, resume treatment at a reduced dose of MK-8353 and selumetinib.
 
• If not resolved in ≤7 days, permanently discontinue MK-8353 and selumetinib.
 

Grade 3 AST or ALT (>5.0 - 8.0 × ULN) AND blood bilirubin ≤2.0 × ULN	Interrupt dose of MK-8353 and selumetinib until resolved to Grade ≤1 (or Grade ≤2 in case of liver metastasis), then: 
 
• If resolved in ≤14 days, maintain dose level of MK-8353 and selumetinib.
 
• If resolved in >14 days, reduce dose level of MK-8353 and selumetinib.
 
 Recurrence: 
 
• Interrupt dosing of MK-8353 and selumetinib until resolved to Grade ≤1 (or Grade ≤2 in case of liver metastasis), then resume treatment at a reduced dose.
 

AST or ALT (>8 x ULN) AND blood bilirubin* ≤ 2.0 × ULN	Permanently discontinue MK-8353 and selumetinib.

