Grade 3	First occurrence: Treatment with MK-8353 and selumetinib should be interrupted. Reassess the participant weekly. Consider referral to dermatologist and manage rash per dermatologist's recommendation. Interrupt treatment until improvement to Grade $\leq 1$ . Resume treatment with MK-8353 and selumetinib at a reduced dose level.  Second occurrence: Interrupt treatment until improvement to Grade $\leq 1$ . Resume treatment with MK-8353 and selumetinib at a reduced dose level. If participant is at the lowest dose, participant should be discontinued. Consider referral to dermatologist and manage rash per dermatologist's recommendation.
Grade 4	Permanently discontinue MK-8353 and selumetinib.
Diarrhea	
Uncomplicated Grade 1-2	Consider temporary interruption of MK-8353 and selumetinib until resolved to Grade $\leq 1$ . Treatment with MK-8353 and selumetinib may then be resumed at the same dose level.
Complicated Grade 1-2	Temporarily interrupt MK-8353 and selumetinib treatment until resolved to Grade $\leq 1$ . Restart MK-8353 and selumetinib at one reduced dose level. If participant is at the lowest dose, participant should be discontinued.
Grade 3-4	Temporarily interrupt MK-8353 and selumetinib treatment until resolved to Grade $\leq 1$ . Restart MK-8353 and selumetinib at a reduced dose level. If participant is at the lowest dose, participant should be discontinued.
Nausea/Vomiting	
Grade 1-2	Treatment with MK-8353 and selumetinib should be maintained at the current dose. Promptly institute antiemetic measure.
Grade 3	Temporarily interrupt MK-8353 and selumetinib treatment until resolved to Grade $\leq 1$ . Resume treatment with MK-8353 and selumetinib at the same dose if, in the judgment of the investigator, the toxicity is considered to be unrelated to selumetinib, or at one reduced dose level.  Note: Interrupt dose for $\geq$ Grade 3 vomiting or Grade 3 nausea only if the vomiting or nausea cannot be controlled with optimal antiemetics (as per local practice).
Grade 4	Permanently discontinue MK-8353 and selumetinib treatment

Interstitial Lung Disease/Pneumonitis	
Grade 1	Maintain dose level of MK-8353 and selumetinib. Monitor weekly.
Grade 2	Withhold MK-8353 and selumetinib for up to 3 weeks. 
 
• If improved to Grade 0 or 1, resume treatment at 1 reduced dose level of MK-8353 and selumetinib
 
• If not resolved within 3 weeks, permanently discontinue MK-8353 and selumetinib.
 

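### Section 5.6 can drop an observed Cycle 1 DLT that 9.5.1 counts, and 6.3.1 can open the next combination before DLT criterion 7 can be resolved

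*Combined protocol and SAP*

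**What the plan says.** **Evaluability.** Section 5.6 lists three kinds of nonevaluable participant, who are replaced and left out of the DLT count. Bullet 2 covers leaving the trial before the safety evaluations are complete for reasons other than treatment-related AEs; it has no DLT exception. Bullet 3 (less than 75% of either drug in Cycle 1) applies only if there was no DLT. Section 9.5.1 includes anyone who finished Cycle 1 without a DLT or had a DLT in Cycle 1, and refers to 5.6 for details. Section 4.3.4 describes the evaluable population as those who finished Cycle 1, and refers to both sections.

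**Timing.** Section 6.3.1 says that in each sequence "a new dose combination will open for enrollment without delay once the 21-day DLT observation" period at the previous level is complete. Section 6.6.2 opens its list with "The occurrence of any of the following toxicities during Cycle 1 will be considered a DLT", but criterion 7 is "Prolonged delay (>2 weeks) in initiating Cycle 2 due to treatment-related toxicity". The same section adds: "The observation window can be modified to encompass Cycle 1 and 2 (and/or additional cycles". Criterion 9 is "Missing >25% of MK-8353 and/or selumetinib doses as a result of drug-related AE(s) during the first cycle".

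**Denominator.** Sections 9.1 and 9.6.2 report the DLT rate and its 80% credible interval among participants treated at the RP2D. The text of 4.3.4 also describes the Table 2 columns as participants treated, while the Table 2 heading and 5.6 count participants evaluable for DLT.

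**The concern.** DLTs are a primary endpoint and the count that drives every Table 2 decision. With cohorts of 3 to 6, one participant can decide the outcome.

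Two rules let a DLT go uncounted when the decision is made. Under 5.6, a participant who has a Cycle 1 DLT and then withdraws consent is removed and replaced, although 9.5.1 keeps that participant. Under 6.3.1, the next combination opens at the end of a 21-day window within which criterion 7 cannot be met. Read literally, a participant whose Cycle 2 is on hold has finished Cycle 1 without a DLT and enters Table 2 as an evaluable non-DLT. In either case the next combination could open on a count that a full application of the plan's own DLT list would not support.

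The denominator question affects only the reported final rate and its interval.

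**Working it through.** **Table 2 reproduced.** Inputs from 4.3.4: target 0.30, Beta(1,1) prior, both epsilons 0.03. With x DLTs in n, the posterior is Beta(1+x, 1+n−x). The decision is the interval among (0, 0.27), (0.27, 0.33) and (0.33, 1) with the largest posterior probability divided by interval length. The DU cutoff is not stated; P(rate > 0.30) > 0.95 is assumed.
- 0/3, Beta(1,4): (1−0.73⁴)/0.27 = 2.65; (0.73⁴−0.67⁴)/0.06 = 1.37; 0.67⁴/0.67 = 0.30. Result E.
- 1/3, Beta(2,3), with F(p) = 6p²−8p³+3p⁴: F(0.27)/0.27 = 0.296/0.27 = 1.10; (0.401−0.296)/0.06, about 1.76 before rounding; (1−0.401)/0.67 = 0.89. Result S.
- All 114 cells match.

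**Section 5.6 against 9.5.1.** Take three participants, one with a Cycle 1 DLT who then withdraws consent.
- 9.5.1: 1/3, S.
- 5.6: 0/2 plus one replacement. The count becomes 0/3, E, if the replacement has no DLT: probability 1−0.30 = 0.70 at the target rate, or 0.50 if the true rate is 50%.

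Withdrawal of consent is the clear case, because 7.1 says that stopping treatment is not withdrawal from the study.

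**Earliest date for criterion 7.** Cycles last 21 days, so Cycle 2 Day 1 is Day 22. Day 22+14 = 36 is exactly two weeks late, so the first whole day beyond two weeks is Day 37. Counted from the edge of the +3-day administrative window in 6.6.3.1, it is Day 25+15 = 40. The window behind 6.3.1 closes on Day 21.

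**Does another criterion catch the case?** Table 4 gives "BID 4 days on and 3 days off". Cycle 1 dosing days are 1–4, 8–11 and 15–18: 12 days × 2 = 24 doses per drug. Criterion 9 needs more than 6 missed. If no earlier dose was missed:

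| Hold starts | Doses missed | Criterion 9 |
|---|---|---|
| Day 15 morning | 8/24 = 33.3% | met |
| Day 15 evening | 7/24 = 29.2% | met |
| Day 16 morning | 6/24 = 25.0% | not met |

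From Day 16 the participant has also received at least 75%, so 5.6 bullet 3 does not apply. Table 7 (6.6.4.1) provides for Grade 2 holds that can exceed two weeks. For pneumonitis it says "Withhold MK-8353 and selumetinib for up to 3 weeks". For AST/ALT it says "Interrupt dose of MK-8353 and selumetinib until resolved to Grade" 1 or lower, with a branch for resolution after 14 days. For rash, the hold runs until Grade 1 or lower with no limit in that row, although 6.4 treats interruptions over 12 weeks as noncompliance. Grade 2 events lie below the Grade 3 threshold of criteria 3 and 4.

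**Effect of one later DLT on E cells.**
- E cells: 12 (x=0, n=3–14) + 9 (x=1, n=6–14) + 4 (x=2, n=11–14) = 25.
- E becomes S: 3 (x=0, n=3–5) + 5 (x=1, n=6–10) + 4 (x=2, n=11–14) = 12. The other 13 stay E.
- In initial cohorts of 3 to 6, four of the five E cells change: 0/3, 0/4, 0/5 and 1/6. Only 0/6 does not.

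**Effect of leaving the held participant out (n falls by 1, x unchanged).**
- S becomes D in 5 cells: 2/4→2/3, 3/6→3/5, 4/9→4/8, 5/11→5/10, 6/13→6/12.
- D becomes DU in 5 cells: 3/5→3/4, 4/7→4/6, 5/10→5/9, 6/12→6/11, 7/14→7/13.
- A cohort of 3 falls to n=2, for which Table 2 has no column.

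**Denominator illustration.** Assume 4 DLTs in 14 evaluable participants and 2 further treated, nonevaluable participants without a DLT. The 80% interval runs from the 10th to the 90th percentile of Beta(1+x, 1+n−x).
- 4/14 = 28.6% (17.2–46.4%).
- 4/16 = 25.0% (15.1–41.6%).

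**The case against.** The strongest reply on timing is that the plan leaves room to wait. Section 6.6.2 lets the DLT window be extended; two cycles are 42 days, which would cover Day 37. Section 4.3.4 bases escalation on ongoing review of safety data, and 8.6.1.2 allows a pause. The trial is open-label, so a Cycle 2 hold is visible from Day 22. The wording in 6.3.1, an allocation section, may mean only that one sequence need not wait for the other. All of this stands, and it rules out a stronger reading that a reader might infer: that the plan obliges escalation over an unresolved toxicity or has no control over it. What remains is that none of these passages gives a trigger for waiting or says how the held participant is counted.

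On 5.6, the case is very narrow: a Cycle 1 DLT, then departure for an unrelated reason before evaluations finish. Section 9.5.1 includes such a participant. That limits the weight, but 9.5.1 offers its definition as an example and points back to 5.6, so the conflict does not resolve itself.

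A reader might also infer that the word treated in 9.1 and 9.6.2 is an error. The documents do not show that. No sentence names the population for that estimate, 9.5.1 assigns safety data to all participants as treated, and 4.3.4 uses the same word loosely for the Table 2 columns. The population is unresolved, which is a lesser point.

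**Conclusion.** The point holds as an inconsistency in counting that should be fixed.

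- **Section 5.6:** bullet 2, as written, can remove an observed DLT. In the three-participant example, S becomes E with probability 0.70 at the target rate. That figure is conditional on the situation arising.
- **Criterion 7:** it cannot be met before Day 37 and does not fit the lead-in of 6.6.2, while 6.3.1 acts at Day 21. The case requires a toxicity hold from Day 16 or later, assuming no earlier missed doses, with no other DLT criterion met. If it occurs, 12 of the 25 E cells are at risk of becoming S.
- **Final rate:** the population is unresolved. The shift from 28.6% to 25.0% rests on an assumed two extra participants and is illustrative only.

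The documents give no basis for saying how often either counting case would occur, so a claim that escalation will commonly be wrong is not supported. The Table 2 effects rest on the printed cells; the assumed DU cutoff was used only to reproduce the table.

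**What to change.** 1. Add to 5.6 bullet 2 the DLT exception that bullet 3 already carries. In 4.3.4, replace the finished-Cycle-1 description with the 9.5.1 definition.
2. Reconcile 6.3.1, 6.6.2 (window, lead-in and criterion 7), 4.3.4 and 9.5.1 so that an E decision does not rest on an unresolved criterion 7 case. Which passage gives way is for the sponsor to settle. Removing the held participant from the Table 2 counts is not a neutral solution: it moves S to D and D to DU in the cells listed above, and under 4.3.4 a DU combination is not explored further.
3. State DLT-evaluable in 9.1, in 9.6.2 and in the 4.3.4 description of the Table 2 columns, because nonevaluable participants without a DLT would dilute the reported rate.

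Items 1 and 3 cost only wording. Item 2 may cost a wait of up to about two weeks (Day 22 to about Day 36), and only when such a hold coincides with one of the 12 cells. Cohorts without a Cycle 2 toxicity hold are unaffected by item 2.

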### **6.3.2 Stratification**

No stratification based on age, sex, or other characteristics will be used in this study.

### **6.3.3 Blinding**

This is an open-label study; therefore, the Sponsor, investigator, and participant will know the intervention administered.

## **6.4 Study Intervention Compliance**

Interruptions from the protocol specified treatment plan or procedures >12 weeks will be considered noncompliant. Further, any interruptions of MK-8353 and selumetinib doses for non-drug related or administrative reasons require consultation between the investigator and the Sponsor and written documentation of the collaborative decision on participant management.

